### **8.2. Setting**

The registry will include comprehensive records on diagnosis, morbidity and management of SAPF, supplied in the form of eCRFs by the participating centers over a period of three years.

The provision of informed consent by the patient or patient's legal guardian will be required for inclusion in accordance with local legal regulations.

The causal SAPF-inducing pathogen will be identified by microbiological examination.

The presence of Protein C deficiency and its contribution to the clinical manifestations of SAPF will be examined upon enrolment by determinations of Protein C concentration and activity, and subsequently documented in the eCRF. Changes in Protein C levels resulting from supplementation will be monitored as well.

The registry will also compare data on the efficacy of therapeutic approaches including or omitting Protein C supplementation.

A further aspect of specific interest is the stratification of outcomes by demographic (e.g. age, sex) and clinical criteria (e.g. morbidity at admission, causal pathogen), in order to identify subgroups of patients with above-average or marginal responsiveness to Protein C supplementation.

The contribution of supportive measures (e.g. assisted ventilation, renal replacement therapy, fluid resuscitation) and co-medication (e.g. vasopressors, corticosteroids, heparin etc.) will be evaluated as well.

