**Flowchart**

Activity / Endpoint	Baseline 	Post-diagnosis period (days)					End of study at hospital discharge or in-hospital death after ICU discharge
		1	3	5	7	ICU discharge or death on ICU after day 7	
Confirm inclusion criteria	x						
Provision of informed consent 	x						
Demographic data collection (incl. ethnic origin)	x						
Risk factors (vaccination status, asplenia) and comorbidities	x						
Estimated time of SAPF onset (hours)	x						
Mortality prediction (APACHE II/SAPS II  or PRISM III  score)	x						
Morbidity assessment (SOFA  /PELOD  score)	x	x	x	x	x		
Laboratory parameters (hematology, coagulation, inflammation)	x	x	x	x	x		
Purpura lesion assessment (c.f. eCRF)	x	x	x	x	x		
Vasopressor use record	x	x	x	x	x	x	
Site, source and origin of infection (including viral)							x
Concomitant causal, supportive and adjunctive treatment (c.f. eCRF)		x	x	x	x	x	
Cumulative dose of blood products and anti-coagulant treatment		x	x	x	x	x	
Antimicrobials		x	x	x	x	x	
Days in ICU							x
Days on mechanical ventilation							x
ECMO and circulatory support systems		x	x	x	x	x	
Days/type on renal replacement therapy							x
Purpura-related surgery (fasciotomy, debridement, amputation)							x
In-hospital mortality assessment		x	x	x	x	x	x
Days in hospital							x
Adverse drug reactions							x

 admission at ICU; according to local regulations APACHE II/SAPS II and SOFA scores will be used in patients aged above 16 PRISM III and PELOD scores will be used in patients aged below 16

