### 8.3. Variables

The selection of the endpoint all-cause in-hospital mortality is justified, in view of the exceptional severity of the disease *per se* and considerable risk associated with the subsequent management of its late sequelae (e.g. reconstructive surgery). On a case-by-case basis, a comparison with the probability of a lethal outcome, as defined by the APACHE II/ SAPS II or PRISM III score, will be made.

Changes in morbidity (as assessed by the SOFA or PELOD indices) will be presented by the difference between scores measured at admission and after 1, 3, 5 and 7 days upon being diagnosed with SAPF ( $\Delta$ SOFA, dPELOD), as well as by the mean total score (SOFA, PELOD) recorded over the observation period of 7 days.

Records will also include description of imminent surgical interventions (during the SAPF treatment), as well as reconstructive measures (skin grafting, amputation).

The sepsis-inducing pathogen and the primarily affected organ will be identified by the results of microbiological examinations and in accordance with clinical manifestations.

Further endpoints comprise the length of stay in the ICU and the total duration of hospitalization (including time of post-SAPF therapy).

Changes in hematological, coagulation and inflammatory parameters will be monitored at selected intervals across the treatment and serve as biomarkers of treatment efficacy or surrogate endpoints, as follows:

- Thrombocyte counts
- Leukocyte counts
- Hemoglobin
- Prothrombin time (PT)
- Activated partial thromboplastin time (aPTT)
- Fibrinogen
- D dimers
- Thrombin-Antithrombin complex (TATc)
- Protein C activity
- Antithrombin III activity
- C-reactive protein (CRP)
- Procalcitonin (PCT)
- Interleukin 6 (IL-6)

Several of these parameters have been used in clinical studies and shown significant changes in the course of therapeutic interventions in sepsis and Purpura fulminans [Bernard et al., 2001; de Kleijn et al., 2003; Schellongowski et al., 2006; Shorr et al., 2008].

Laboratory indices of organ dysfunction are confined to measurements of

- Glucose
- Lactate
- Creatine kinase

Recording of adverse events related to the treatment of SAPF is left at the discretion of the local site investigator (c.f. comment in 9.9. *Limitations of research methods*); the emphasis is laid on

- bleeding incidents
- thrombotic events

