#### 8.4. Data sources

Registry subjects will be identified by the participating centers. The recruitment will be primarily based on the concomitant presence of clinical signs of sepsis and *Purpura fulminans*. Clarification of the underlying etiopathogenesis will be performed *post hoc*, upon collection of additional clinical and laboratory data.

Data capture comprises assessment at baseline and at several intervals of 24 (initially) and 48 (subsequently) hours for an overall period of 7 days, while in ICU. A final appraisal of the patient's status will take place at the time point of discharge from the hospital.

The exposure to individual therapeutic agents will be deduced from doses and frequency of application during the period spent in ICU.

The influence of potential confounding variables and effect modifiers (e.g. concomitant anticoagulant medication, fluid resuscitation, renal replacement therapy etc.) will be extrapolated from the corresponding specific entries in the eCRF.

The outcome indicators have been previously validated and are routinely used.

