## 8.7. Data analysis

A binary logistic regression model will be fitted for the all-cause in hospital mortality to compare the efficacy of the different treatments (e.g. with or without Protein C supplementation). To adjust for confounders, causal pathogen, baseline Apache II (PRISM III) score, laboratory parameters, age, sex, co-medication etc. can be included as covariates in this model.

Consecutive changes in SOFA or PELOD scores ( $\Delta$ SOFA, dPELOD) at individual post-diagnosis intervals and their mean values calculated for the observation period of 7 days will be compared to the scores determined on admission (baseline). Changes in these organ failure indices will be examined by means of

- Paired samples T-test
- Linear model with morbidity score baseline adjustment and alternative co-variables (e.g. hematological, coagulation or inflammatory parameters)

Explorative analysis without correction and with a pre-set level of significance of 0.05 will be conducted as well.

All endpoints will be subjected to descriptive statistical analysis with determination of 95-percent confidence intervals. Between-group comparisons will be preceded by distribution analysis (Shapiro-Wilk Test of normality). Depending on the data distribution, *post hoc* processing will involve either parametric (one-way ANOVA, T test) or non-parametric (Kruskal-Wallis, Mann-Whitney U-test) approaches.

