## 8.9. Limitations of the research methods

The selected endpoints are routinely used and the methodologies for their assessment have been comprehensively verified and proved to display predictive strength. However, it should be taken into consideration that the inherent high mortality risk might compromise the validity of mortality as a major endpoint. Simultaneous use of composite outcomes is deemed to ameliorate the assessment of the effects of therapeutic interventions [Goldstein et al., 2005; Nadel et al., 2007].

The current approach to scoring the severity of purpura-associated lesions employs arbitrary statements, which reflect the investigator's day-to-day impression [de Kleijn et al., 2003]; accordingly, large variations and limited possibility for quantitative comparisons should be expected. A descriptive lesion grading of the external appearance based on pictorial reference examples in the eCRF it is expected to provide at least a uniform description.

The endpoint 'length of hospital stay' will conceivably display large inter-individual variability, due to varying length of post-ICU recovery and immediately adjacent reconstructive surgical interventions. Nonetheless, this variable is expected to deliver important information on the economic burden of SAPF and its direct sequelae.

Despite encouraging evidence, the relevance of biochemical markers of inflammation in monitoring the effects of therapeutic interventions in sepsis remains ambiguous, mainly due to issues of sensitivity and specificity [Goldstein et al., 2005]. Still, in view of the undisputed role of inflammatory mediators in the pathogenesis of SAPF [Darmstadt, 1998], their measurement is justifiable.

The therapy of SAPF involves multi-pronged measures, which may obscure the "net effect" of an individual therapeutic agent. Thus, efficacy aspects of a given treatment have to be evaluated in conjunction with the co-medication used in the individual case; this circumstance, as well as the influence of concomitant medication, will be taken into consideration while designing the eCRF.

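### Protein C exposure taken over the whole ICU stay, in a mortality model with no time zero, lets immortal-time bias push the odds ratio towards benefit

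*Combined protocol and SAP*

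**What the plan says.** Section 8.7 names one model for mortality, a binary logistic regression for all-cause in-hospital death that compares treatments, for example with and without Protein C. On covariates it says: "To adjust for confounders, causal pathogen, baseline Apache II (PRISM III) score, laboratory parameters, age, sex, co-medication etc. can be included as covariates".

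The exposure rule is in 8.4: "The exposure to individual therapeutic agents will be deduced from doses and frequency of application during the period spent in ICU". Section 8.5 expects that showing differences may require a two-way split, with use or omission of Protein C as its example. No section gives a start time, grace period, landmark or time-dependent term.

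On laboratory values, the flowchart row "Laboratory parameters (hematology, coagulation, inflammation" is marked at baseline and at Days 1, 3, 5 and 7. Section 8.3 says: "Changes in hematological, coagulation and inflammatory parameters will be monitored at selected intervals across the treatment and serve as biomarkers of treatment efficacy", or as surrogate endpoints. Section 8.2 adds: "Changes in Protein C levels resulting from supplementation will be monitored as well".

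On co-treatment, the flowchart has a baseline vasopressor record. The other concomitant treatments start at Day 1, and days on renal replacement have their own row only at end of study. Section 8.9 states that "efficacy aspects of a given treatment have to be evaluated in conjunction with the co-medication used in the individual case".

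On the clock, the flowchart footnote sets baseline at ICU admission, but its day columns are headed as post-diagnosis. Section 8.3 mixes the two: "difference between scores measured at admission and after 1, 3, 5 and 7 days upon being diagnosed with SAPF". Section 8.4 describes capture at baseline and then at 24-hour and later 48-hour intervals.

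**The concern.** Patients who die early have less time in which to receive Protein C. If treated means any dose during the ICU stay, survival to the first dose is built into the treated group, and the earliest deaths collect in the untreated group. In a disease with mortality above 50% (section 6), a treatment that does nothing can then look protective. Larger accrual does not remove this.

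The covariate wording adds a smaller risk. A laboratory value taken after Protein C has started may lie on the path from treatment to outcome. Adjusting for it can remove part of the effect that the model is meant to estimate.

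The comparison matters: 8.1 puts particular emphasis on it, and under section 11 the Advisory Committee bases treatment recommendations on the biannual evaluations. The limitations in 8.9 do not mention time zero, so a reader would not be warned.

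**Working it through.** The plan states no effect size, power or calculated sample size, so there is no figure of its own to reproduce. The timings below are assumptions; the documents give none.

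**1. The mechanism by hand, no true effect.** Assume 60% of patients are intended for Protein C whatever their prognosis, time to start is exponential with mean s days, time to death among non-survivors is exponential with mean m days, and survivors stay in ICU for 3 days plus an exponential time with mean 10.

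- P(treated | died) = 0.6 × m/(m + s)
- P(treated | survived) = 0.6 × [1 − exp(−3/s) × s/(s + 10)]
- OR = odds of treatment among deaths ÷ odds of treatment among survivors. Overall mortality cancels out.

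| m | s | P(treated, died) | P(treated, survived) | OR |
|---|---|---|---|---|
| 7 | 0.25 | 0.579 | 0.600 | 1.377/1.500 = 0.92 |
| 4 | 1 | 0.480 | 0.597 | 0.923/1.483 = 0.62 |
| 2 | 2 | 0.300 | 0.578 | 0.429/1.368 = 0.31 |

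Simulation of the same set-up gives the same three values. With a 24-hour landmark, P(treated by 24 h) = 0.6 × [1 − exp(−1/s)] in both outcome groups, so the OR is 1; simulated values are 0.99 to 1.01.

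**2. With confounding by severity.** Inputs, 400,000 patients per setting:
- severity L ~ N(0,1)
- death without Protein C ~ expit(0.2 + 1.2L), giving 54% deaths
- mean time to death 2, 4 or 8 days
- Protein C intended ~ expit(0.7L), and started only if the patient is alive
- start uniform in the first day for a share of 0.5, 0.8, 0.95 or 1.0, otherwise uniform over days 1 to 7

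Both models adjust for L.

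| True OR | Any dose in ICU | Day 1 landmark |
|---|---|---|
| 1.0 | 0.31 to 0.87 | 0.98 to 1.02 |
| 0.50 | 0.16 to 0.44 | 0.50 to 0.63 |

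Even when every start falls in the first 24 hours, the null case reads 0.64 to 0.88. If deaths in the first 12 hours never enter the registry, it reads about 0.40 to 0.96. The landmark's drift from 0.50 to 0.63 is dilution by later starters, who form 0 to 27% of the Day 1 unexposed group.

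**3. What the landmark leaves out.** The share of deaths before 24 h is 1 − exp(−1/m): 39%, 22% and 12% for m = 2, 4 and 8. Multiplied by 54% mortality, that is 21%, 12% and 6% of patients. At 150 patients (50 per year × 3 years) the SE of the log OR goes from 0.392 to 0.403 (+3%) in the mildest setting and from 0.429 to 0.507 (+18%) in the worst.

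**4. Later laboratory values.** The 13 haematology, coagulation and inflammation parameters in 8.3 at five times give 13 × 5 = 65 values per patient, of which 13 × 4 = 52 come after baseline. This counts what is collected, not what the model will use. In a simulation with an OR of 0.51 to 0.52 adjusted for baseline severity, adding a Day 3 value gives 0.47, 0.63 or 0.86 when 0, 50 or 100% of the effect passes through it. Under the timings in step 2, 1 − exp(−3/m) = 31 to 78% of deaths occur before Day 3 and have no such value.

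**5. Co-treatment.** If it is started together with Protein C (true OR 0.50), leaving it out gives 0.40 to 0.64 and including it 0.49 to 0.50. If it is a consequence of Protein C's effect (OR 0.51 without it), including it gives 0.49, 0.55 or 0.61 at the same three mediated shares. Neither choice is always right.

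**The case against.** The strongest reply is that the plan commits to less than this reading assumes. Any-dose coding is an inference: 8.4 speaks of doses and frequency, the flowchart records cumulative dose by visit, and 8.5 is hedged. A time-aware exposure could be built from those records. That is true, but no section says it will be, and the exposure window, two-way split and logistic model that are written down lead to the biased coding.

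Section 9 seeks consent before enrolment, with local exceptions, so some very early deaths may never enter. That weakens the bias, as the 0.40 to 0.96 range shows, but does not remove it.

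The covariates are listed as confounders, and baseline may be meant to cover the whole list. This is a fair reading, which is why the laboratory point is secondary. Adjusting for co-medication is defensible under 8.9, and the eCRF, which is not visible, may hold more timing detail than the flowchart.

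A reader might infer that 8.7 pools raw APACHE II and PRISM III points under one coefficient. The text does not say so; the bracket can mean whichever score applies by age. If points were pooled alongside linear age, the null OR would be 0.98 to 1.20 over 27 assumed settings, at most 1.10 in 20 of them. Other assumed score distributions gave 1.04 to 1.29. At 150 patients, separate scaling did not reduce root mean squared error in 16 of the 27 settings.

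A landmark also removes early deaths from an all-cause mortality comparison. That is a real cost.

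**Conclusion.** The exposure point holds. Followed as written, with use or omission defined over the ICU stay, the main comparison is biased towards benefit; under the assumed timings a null effect reads 0.31 to 0.87, or about 0.40 to 0.96 without the first 12 hours of deaths. These ranges rest on assumed start and death times and illustrate size; they are not estimates for this registry. The low end is an extreme corner.

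The laboratory point is a lesser gap: the text permits adjustment for later values but does not plan it.

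A reader might also infer that the registry's final odds ratio must overstate benefit. The documents do not support that. Adjustment for later laboratory values can pull towards no effect, and residual severity confounding can pull towards harm if sicker patients are treated more often. Only the direction of the immortal-time component is known.

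**What to change.** 1. **Exposure.** For the main mortality comparison, classify Protein C by the Day 1 record among patients alive at that record, and keep later starters in their Day 1 group. Report earlier deaths by treatment received, and the number of later starters. Show the whole-stay comparison only as a secondary result labelled as subject to immortal-time bias. If the eCRF holds start times, a time-dependent exposure analysis using all deaths is an alternative or a sensitivity analysis.
2. **Clock.** State one origin for Day 1, reconciling ICU admission as baseline (flowchart footnote), days counted from diagnosis (flowchart, 8.3) and the 24- and 48-hour intervals (8.4).
3. **Covariates.** In the main model use laboratory values and vasopressor use at baseline only, and flag patients whose Protein C began before the baseline sample. Exclude later laboratory values and end-of-study renal replacement days. Because of 8.9, also report the model with co-treatments recorded by the landmark. Fix both models in advance and say that neither removes all bias.
4. **Optional.** Enter severity as the logit of the predicted probability of death from the patient's own instrument, plus an age-group indicator. Section 8.3 already plans that probability case by case: "a comparison with the probability of a lethal outcome, as defined by the APACHE II/ SAPS II or PRISM III score, will be made". The gain at about 150 patients is small.

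This changes analysis wording and needs no new data, provided the eCRF identifies Protein C use by the Day 1 record. Under the assumed timings, the main result applies to patients alive at Day 1, leaving out 6 to 21% of patients and 12 to 39% of deaths; a true OR of 0.50 can read up to about 0.63; and the SE rises by about 3 to 18%. The order of Protein C and co-treatment within Day 1 may stay unknown.

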Endpoints	
 
• All-cause in-hospital mortality
 
• Morbidity at defined post-diagnosis intervals and over 7 consecutive days 
 
- Mean total SOFA score (age <math>\geq 16</math>)
 
- PELOD score (age <math>< 16</math>)
 
- <math>\Delta</math>SOFA or dPELOD score for day-to-day comparisons
 
 
 
• Extent and severity of Purpura lesions
 
• Need for reconstructive surgery (amputations, skin grafts)
 
• Length of ICU stay (days)
 
• Length of hospital stay (days)
 
• Changes in hematological parameters 
 
- WBC count
 
- Thrombocyte count
 
- Hemoglobin
 
 
 
• Changes in coagulation parameters 
 
- Prothrombin time (PT)
 
- Activated partial thromboplastin time (aPTT)
 
- Fibrinogen
 
- D-dimers
 
- Thrombin-antithrombin complex (TATc)
 
- Protein C activity
 
- Antithrombin III activity
 
 
 
• Changes in inflammatory parameters 
 
- C-reactive protein (CRP)
 
- Procalcitonin (PCT)
 
- Interleukin 6 (IL-6)
 
 
 
• Changes in organ dysfunction parameters 
 
- Glucose
 
- Lactate
 
- Creatine kinase (CK)
 
 
 
• Duration of mechanical ventilation (days)
 
• Duration of renal replacement therapy (days)
 
• Vasopressor use (days/doses)
 
• Sepsis-inducing pathogen
 
• Adverse event related to PF treatment (reporting as per decision of the investigator) 
 
- Bleeding
 
- Thrombotic events
 
 
 

Inclusion criteria	
 
- Diagnosis of severe sepsis and Purpura fulminans
 
- Signed informed consent (according to local legal regulations)
 

Exclusion criteria	
 
- premature neonates (<math>< 36</math> gestational week)
 

Centers	Approx. 30 participating centers in Germany, Austria, Ireland, UK, Italy, Spain, Netherlands (selected centers)

Timetable	First patient in	Q3 2015
	Registry duration	3 years, with an option of prolongation
	Estimated enrolment	Approx. 50 patients/year
	Interim Analysis	Biannually

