## 6. Rationale and background

*Purpura fulminans* is a life-threatening and highly disabling condition characterized by rapidly evolving thrombosis in the dermal and systemic microcirculation. The estimated incidence of the disease is 0.1 per 100,000 inhabitants [Nicolas and Debonne, 2002]. It is associated with high mortality (above 50 %), owing to progressive cutaneous hemorrhage and multiple organ dysfunction. Profound tissue lesions and grave disturbance in numerous vital functions also determine a considerable long-term morbidity and disability.

Apart from a few cases of idiopathic origin, the etiology of *Purpura fulminans* is ascribed to either congenital abnormality or acquired deficiency of Protein C-operating anticoagulant pathways. The latter condition is in the vast majority secondary to an acute severe infection, thus coining the term sepsis-induced or sepsis-associated *Purpura fulminans* (SAPF) [Betrosian et al., 2006]. Several bacterial pathogens can induce SAPF, with meningococcal and pneumococcal infections accounting for the majority of cases. Causal involvement of viral and protozoan pathogens also has been described [Betrosian et al., 2006].

The pathogenesis of SAPF exemplifies the induction of a coagulopathy by the intertwined action of extrinsic bacterial (e.g. endotoxins) and intrinsic (e.g. vascular, inflammatory and hematologic) factors. The decay of endogenous anti-coagulant systems has a decisive contribution to the imbalance of clotting in sepsis and the presence of a consumptive coagulopathy is a distinct feature of infection-associated *Purpura fulminans* [Darmstadt, 1998]. Extensive similarities with clinical and pathological characteristics of *Purpura fulminans* in congenital Protein C deficiency have brought this endogenous anti-coagulant into focus with regard to the pathogenesis of SAPF [Francis, 1990]. Indeed, SAPF reflects an exaggerated pro-coagulant response resulting from decreased abundance/activity of endogenous anticoagulants, such as antithrombin and Protein C [Dempfle,

2004]. Meanwhile, ample evidence has accumulated in support of the view that circulating Protein C concentrations markedly decline in severe sepsis, due to both, suppressed biosynthesis and increased consumption/degradation [Fourrier et al., 1992; Leclerc et al., 1992; Borgel et al., 2006; Shorr et al., 2006].

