#### 8.5. Study size

Earlier reports on the incidence of SAPF [Darmstadt, 1998; Nicolas and Debonne, 2002] were based on the association of the condition with meningococcal sepsis. Conceivably, these data hardly permit extrapolation to the contemporary situation, which has substantially changed after the introduction of meningococcal vaccination [Maat et al., 2007]. Depending on the number of participating centers, a realistic forecast envisages the recruitment of 50 to 70 adult and pediatric patients during the first year of the registry, with subsequent possible increase to 100 per year. In view of the spread of meningococcal vaccination among children and adolescents, the expected proportion of adult patients might eventually exceed 50 %.

With regard to the relatively limited projected study size, and with regard to the lack of a uniform treatment concept for SAPF, demonstration of differences between individual treatment paradigms might require dichotomization (e.g. use vs. omission of Protein C supplementation) and could be applicable only to selected endpoints.

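### The mortality model has an open covariate list and no sparse-data method, so at about 150 patients a full ordinary fit would overstate a real Protein C effect and reject too often

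*Combined protocol and SAP*

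**What the plan says.** Section 8.7 names one method for mortality: "A binary logistic regression model will be fitted for the all-cause in hospital mortality to compare the efficacy of the different treatments". Use against non-use of Protein C is its example of the contrast. On adjustment it says that "causal pathogen, baseline Apache II (PRISM III) score, laboratory parameters, age, sex, co-medication etc. can be included as covariates in this model". The wording is permissive and the list is open. No coding, maximum number of terms, selection rule, penalisation or plan for separation is given.

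The size of the list has to be read from other sections. Section 8.3 says "Changes in hematological, coagulation and inflammatory parameters will be monitored at selected intervals across the treatment" and names 13 markers. A further three (glucose, lactate, creatine kinase) follow the sentence beginning "Laboratory indices of organ dysfunction are confined to measurements of". Section 8.2 refers to "co-medication (e.g. vasopressors, corticosteroids, heparin etc", which is again open. No pathogen categories are defined; section 6 describes "meningococcal and pneumococcal infections accounting for the majority of cases".

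On size, the abstract expects "Approx. 50 patients/year" for three years, with possible prolongation. Section 8.5 forecasts 50 to 70 patients in the first year and possibly 100 a year after that. It concedes a "relatively limited projected study size" and responds by simplifying the treatment contrast and restricting the endpoints. It does not connect size with the number of covariates.

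**The concern.** Maximum-likelihood logistic regression with few outcomes per parameter pushes non-null coefficients away from zero. It also gives standard errors that are too small, so intervals are too narrow and tests reject too often. The plan permits a model in that range and has no safeguard against it. Because the list is open, covariates could also be chosen after the results are seen.

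The with-or-without Protein C comparison is a stated aim in section 7. Under section 11, registry evaluations feed therapy recommendations that go to the centers and to outside parties. A benefit or harm overstated by a quarter or more on the log scale would carry into that advice.

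**Working it through.** The plan states no power, event target or parameter count, so there is no figure of its own to reproduce.

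**Parameters.**
- Treatment 1, pathogen 3 (four levels assumed), severity score 1, age 1, sex 1, laboratory 13, co-medication 5 (assumed): 1 + 3 + 1 + 1 + 1 + 13 + 5 = 25.
- With two pathogen terms, all 16 markers and only the three named co-medications: 1 + 2 + 1 + 1 + 1 + 16 + 3 = 25 again.
- The first count with 16 markers gives 28; further terms take it to about 31. A selective reading gives about 10.

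**Rarer outcome class.** Sections 4 and 6 put mortality above 50%, so the survivors are the rarer class.
- Abstract: 50 × 3 = 150 patients. The rarer class is 75 at 50% mortality, 67.5 at 55% and 60 at 60%. Per parameter: 60/25 = 2.4 to 75/25 = 3.0.
- Section 8.5, upper forecast: 50 + 100 + 100 = 250 to 70 + 100 + 100 = 270 patients. The rarer class is 250 × 0.40 = 100 to 270 × 0.50 = 135. Per parameter: 4.0 to 5.4.

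**Simulation.** Assumptions that are not in the documents: about 40% on Protein C, covariate correlation 0.2, mild confounding, six prognostic covariates with effects from none to strong, true odds ratio 1.0 for error and 0.5 or 0.6 for bias, and two-sided tests at 0.05. Mortality was 50% to 60%. The ranges cover separate sets of runs with differing settings.

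| Patients | Parameters | Fit | Excess in log-OR | Error at nominal 5% |
|---|---|---|---|---|
| 150 | 25 | ordinary | 24% to 51% | 5.9% to 9.1% (Wald); 8.8% to 10.8% (likelihood ratio) |
| 150 | 10 | ordinary | 10% to 12% | 5.5% to 6.3% (one likelihood-ratio result 6.6%) |
| 150 | 6 | ordinary | 6% to 7% | about 5.5% to 6% |
| 250 to 270 | 25 | ordinary | 13% to 14% | 5.3% to 6.6% |
| 150 | 25 | Firth | 1% to 2.5% | 4.9% to 5.5% (profile) |
| 270 | 25 | Firth | under 1% | 5.6% (profile) |
| 150 | 8 | Firth | about 2% | 3.9% to 4.7% |

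An example at 150 patients, 25 parameters, 60% mortality and true odds ratio 0.5: the mean log-OR is -0.902 against -0.693, and 0.902/0.693 = 1.30. The median reported odds ratio is 0.425. With strong covariate effects at 50% mortality, the mean is -1.046 (ratio 1.51) and the median odds ratio 0.38. With a true odds ratio of 1.0, the mean log-OR stays within about 0.01 of zero.

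The ordinary fit also misstates its precision. At a true odds ratio of 0.6 with 25 parameters and 150 patients, the empirical SD was 0.52 to 0.57 against a model standard error of 0.46 to 0.48. The eight-parameter Firth model had an SD of 0.39.

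Monte Carlo error for a 5% rate over 1,500 runs is √(0.05 × 0.95/1500) = 0.56 percentage points. The bias is therefore the firm result. The excess error is clear for most 25-parameter settings at 150 patients and small with 10 parameters.

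**The case against.** The plan obliges nobody to fit 25 parameters. The covariates are optional, and a sensible analyst might use ten or fewer, where the distortion is modest. Section 8.5 allows for up to about 270 patients and the abstract for prolongation; both shrink the problem. The flowchart's laboratory row covers hematology, coagulation and inflammation, so 13 markers is a better-supported count than 16. Penalisation is not named, but neither is it ruled out. All of this stands, and it is why the result is given as a range. It does not remove the point: nothing in section 8.7 keeps the model small, and the higher enrolment is only a possibility.

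Four stronger readings are tempting, and the documents do not support them.
- That the listed covariates require 25 parameters. They are only permitted.
- That the Protein C odds ratio will be exaggerated whatever the truth. With no true effect there is no bias, only wider spread and more false positives.
- That the full model will be run at every biannual report, on very few patients. Interim analyses and reports are announced, but no section says that this model is part of each.
- That patients with any missing laboratory value will be dropped. No complete-case rule is stated, and section 8.6 flags missing values for correction at entry.

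**Conclusion.** The concern holds in conditional form. If most listed covariates enter an ordinary fit at about 150 patients, a non-null Protein C log-OR is about 25% to 50% too large and the nominal 5% test runs at roughly 6% to 11%. At 10 parameters, or at 250 to 270 patients, the distortion falls to about 10% to 14% on the log scale, with error of about 5% to 7%. The figures rest on the assumed Protein C share, covariate correlation, prognostic strength and coding of pathogen and co-medication.

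An open list alone would be a lack of detail. What makes this worth changing is that a better fitting method exists at almost no cost: with the same 25 covariates, Firth's method nearly removes the bias and brings the error close to 5%. It deals with sparse-data bias only. Confounding by indication remains and depends on which covariates are kept.

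**What to change.** In section 8.7, state that in-hospital mortality will be analysed by logistic regression fitted with Firth's penalised likelihood, with confidence intervals and tests from the profile penalised likelihood. Wald tests should not be used with it: in the 25-parameter runs at 150 patients they rejected only 3.1% to 4.1% of null cases.

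Fix a short baseline covariate set in advance: severity score, age, pathogen group and baseline Protein C activity. With treatment and a four-level pathogen group this is 1 + 1 + 1 + 3 + 1 = 7 parameters, provided that the adult and pediatric scores are put on a common scale; the text should say how. Baseline Protein C activity should stay in. Section 8.2 singles it out at enrolment, and it plausibly influences who receives supplementation, so dropping the whole laboratory panel would risk confounding. The fuller laboratory and co-medication set becomes a named sensitivity analysis, also with Firth's method.

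The cost is analysis text and a standard software option, with no new data. The main model carries fewer covariates. Nominal rejection rates are lower: with 25 parameters, 150 patients and a true odds ratio of 0.5, the profile test rejected in 46.1%, 34.7% and 24.9% of runs as covariate strength rose, against 51.8%, 41.6% and 34.2% for the ordinary Wald test. Part of the ordinary fit's higher rate comes from its excess error and inflated estimate.
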